9.2 Subject Accountability

The number of subjects screened, enrolled, receiving IP, and completing the study will be summarized. Key study dates for the first subject enrolled, last subject enrolled, last subject's end of study **for primary analysis and for interim analysis** will be presented. **For the interim analyses, the numbers of ongoing subjects and the data cut-off date will also be presented.**

Study discontinuation and IP discontinuation will be tabulated separately by reasons for discontinuation.

The number of subjects included in and excluded from the full analysis set and reason for exclusion will also be summarized.

9.3 Important Protocol Deviations

Important Protocol Deviations (IPDs) categories are defined by the study team before the first subject's initial visit and updated during the IPD reviews throughout the study prior to database lock. These definitions of IPD categories, subcategory codes, and descriptions will be used during the course of the study. Eligibility deviations are defined in the protocol. **In addition, COVID-19 related protocol deviations will also be summarized and listed.**

9.4 Demographic and Baseline Characteristics

The descriptive statistics of baseline characteristics will summarize the following: baseline characteristics, demographics, cardiovascular medical history, laboratory parameters, and lipid-regulating concomitant medications.

9.5 Efficacy Analyses

9.5.1 Analyses of Primary Efficacy Endpoint(s)

Not applicable.

9.5.2 Analyses of Secondary Efficacy Endpoint(s)

Descriptive statistics of percent change from baseline will be provided for the following efficacy parameters at week 80

- LDL-C
- Non-HDL-C
- ApoB
- Total cholesterol/HDL-C ratio
- ApoB/ApoA1 ratio

In addition, the descriptive statistics in change from baseline will be provided for LDL-C at week 80.

9.5.3 Analyses of Exploratory Efficacy Endpoint(s)

Descriptive statistics summarized by 3-level groups will be provided for actual value, change from baseline and percent change from baseline at each protocol-specified visit in the following

- LDL-C
- Total cholesterol
- Non-HDL-C

- ApoB
- Total cholesterol/HDL-C ratio
- ApoB/ApoA1 ratio
- Triglycerides
- VLDL-C
- HDL-C
- ApoA1
- Lp(a)

Descriptive statistics will be provided for actual value and change from baseline at each protocol-specified visit in the following

- Proprotein convertase subtilisin/kexin type 9 (PCSK9)
- High sensitivity C-reactive protein (hsCRP)

In addition, a shift table for hsCRP will also be provided, for levels at baseline to maximum post-baseline value (<1, 1-3, >3 **mg/L**)

9.6 Safety Analyses

9.6.1 Analyses of Primary Safety Endpoint(s)

Subject incidence of treatment emergent adverse events at week 80 **will be summarized.**

9.6.2 Adverse Events

The Medical Dictionary for Regulatory Activities (MedDRA) version 22.0 or later will be used to code all events categorized as adverse events to a system organ class and a preferred term. Severity of AEs will be graded using the CTCAE ([Appendix B](#)) and recorded on the eCRF.

The subject incidence of adverse events will be summarized for all treatment-emergent adverse events, serious adverse events, adverse events leading to withdrawal of investigational product and fatal adverse events.

Subject incidence of all treatment-emergent adverse events, serious adverse events, adverse events leading to withdrawal of investigational product and fatal adverse events will be tabulated by system organ class and preferred term in alphabetical order.

In addition, summaries of treatment-emergent and serious adverse events occurring in at least 1% of the subjects by preferred term will be provided in descending order of frequency.

Subject incidence of adverse events associated with lipid lowering therapies:

- **Injection site reactions**
- **Hypersensitivity or allergic reactions**

will be summarized by category and preferred term.

Subject neurocognitive events will also be summarized.

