To date, 15 subjects < 18 years of age and with HoFH or compound HeFH have been enrolled in Studies 20110233 and 20110271; 10 participated in both studies, 4 participated only in Study 20110271, and 1 participated only in Study 20110233. Per protocol, of the 14 subjects participating in Study 20110271, the non-apheresis subjects ($n=10$) began the study on 420 mg QM, while the apheresis subjects ($n=4$) began the study on 420 mg Q2W. In general, no differences in the safety profile have been seen in pediatric subjects relative to adults. In Study 20110271, as of 01 July 2014, the subject incidences of treatment emergent adverse events and serious adverse events were 71% and 14% among adolescents, compared to 68% and 10% among all subjects with HoFH. Average exposure to evolocumab was longer among adolescents, median 11.4 months vs 7.5 months in adults with HoFH. Among pediatric subjects, a total of 28 adverse events were reported. All but 2 of these events were deemed non-serious and were Common Terminology Criteria for Adverse Events (CTCAE) grade 1 or 2. The 2 serious adverse events (worsening of chest pain and occlusive coronary artery disease) were both CTCAE grade 3 and unrelated to investigational product (IP), and are both known consequences of the subjects' underlying FH.

Approved

The dose of 420 mg evolocumab SC was selected based on pharmacokinetic modeling for this pediatric age group (Section 2.4) and is supported by the current safety experience with the same dosing in pediatric subjects in Studies 20110233 and 20110271.

As in adult studies, the subjects in this study will be monitored for the development of anti-evolocumab antibodies. To date, the overall immunogenicity rate is < 1% and the formation of neutralizing anti-evolocumab antibodies has not been observed.

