2.5 Clinical Hypotheses

The primary hypothesis is that SC evolocumab will be well tolerated when added to standard of care in pediatric subjects 10 to 17 years of age with HeFH or HoFH.

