9.2 Safety Event Reporting Procedures

9.2.1 Adverse Events

9.2.1.1 Reporting Procedures for All Adverse Events (Serious or Non-serious Adverse Events)

Refer to [Sections 9.2.1.2](#) and [9.2.1.3](#) for additional information regarding the reporting of serious adverse events.

For subjects enrolling in Study 20120124 after completion of Study 20120123 (HeFH subjects) the investigator is responsible for ensuring that all adverse events and all adverse device effects observed by the investigator or reported by the subject that occur after the first dose of investigational product/study treatment/protocol-required therapies through the end of Study 20120124 are reported using the Event CRF.

For subjects not rolling over from Study 20120123 (HoFH subjects), the investigator is responsible for ensuring that all adverse events possibly related to study procedures, adverse device effects, and serious adverse events are reported from signing of the ICF. All other adverse events are reported that occur after enrollment. The investigator is responsible for ensuring that all adverse events observed by the investigator or reported by the subject that occur from signing of the ICF or that occur after enrollment through the end of Study 20120124 are reported using the Event CRF.

The investigator must assign the following adverse event attributes:

- adverse event diagnosis or syndrome(s), if known (if not known, signs or symptoms),
- dates of onset and resolution (if resolved),
- severity,
- assessment of relatedness to investigational product (evolocumab and/or the device[s]: the prefilled AI/Pen or AMD), or other protocol-required therapies, protocol-required procedure or activity, and
- action taken.

The adverse event grading scale used will be the National Cancer Institute (NCI) Common Terminology Criteria for Adverse Events (CTCAE). The grading scale used in this study is referenced in [Appendix A](#).

If the severity of an adverse event worsens from the date of onset to the date of resolution, record a single event for each increased level of severity on the Adverse Event Summary CRF.

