The investigator must assess whether the adverse event is possibly related to IMP (evolocumab). This relationship is indicated by a “yes” or “no” response to the question: Is there a reasonable possibility that the event may have been caused by evolocumab (investigational medicinal product)? The investigator must assess whether the adverse event is possibly related to the prefilled AI/Pen or the AMD (investigational device(s) used to administer evolocumab). The relationship is indicated by a “yes” or “no” response to the question: Is there a reasonable possibility that the event may have been

caused by the investigational device? Relatedness means that there are facts or reasons to support a relationship between IP and the event.

The investigator must assess whether the adverse event is possibly related to any study-mandated activity (eg, administration of investigational product, protocol-required therapies, device(s) and/or procedure (including any screening procedure(s))). This relationship is indicated by a “yes” or “no” response to the question: “Is there a reasonable possibility that the event may have been caused by a study activity (eg, administration of investigational product, protocol-required therapies, device(s)), and/or procedure”?

The investigator is responsible for reviewing laboratory test results and determining whether an abnormal value in an individual study subject represents a clinically significant change from the subject’s baseline values. In general, abnormal laboratory findings without clinical significance (based on the investigator’s judgment) are not to be recorded as adverse events. However, laboratory value changes that require treatment or adjustment in current therapy are considered adverse events. Where applicable, clinical sequelae (not the laboratory abnormality) are to be recorded as the adverse event.

The Investigator is expected to follow reported adverse events until stabilization or reversibility.

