10.4.2 Primary Endpoint

The current Medical Dictionary for Regulatory Activities (MedDRA) version at the time of the data lock will be used to code all adverse events (AE) to a system organ class and a preferred term. The following analyses will be performed on FAS.

Treatment emergent adverse events will be tabulated by system organ class and preferred term at week 80. Tables of fatal adverse events, serious adverse events, device related adverse events, adverse events leading to withdrawal from investigational product, and significant treatment-emergent adverse events will also be provided.

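### No adverse event table in SAP 9.6.1–9.6.2 uses CTCAE grade or relatedness to evolocumab, though both are recorded for every event, and two adverse event tables promised in the protocol are missing from the SAP

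*SAP*

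**What the plan says.** **What is collected.** Protocol 9.2.1.1 states that "The investigator must assign the following adverse event attributes"; the list includes severity and relatedness. Severity is graded on the CTCAE. For each event the investigator answers yes or no to "Is there a reasonable possibility that the event may have been caused by evolocumab (investigational medicinal product", and a separate question asks the same about the injection device. SAP 9.6.2 confirms the first attribute: "Severity of AEs will be graded using the CTCAE", with the grade entered on the eCRF.

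**What is tabulated in the SAP.** Section 9.6.1 gives subject incidence of treatment-emergent adverse events (TEAEs) at week 80. Section 9.6.2 then says "The subject incidence of adverse events will be summarized for all treatment-emergent adverse events, serious adverse events, adverse events leading to withdrawal"; withdrawal here means stopping the study drug, and deaths form the fourth category. The same four categories are repeated by system organ class and preferred term (SOC/PT). There are also lists of TEAEs and serious events reaching 1% by preferred term, tables of injection site reactions and of hypersensitivity, and a summary of neurocognitive events.

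**What the protocol adds.** The synopsis and section 10.4.2 also promise a table of device related events and state that "significant treatment-emergent adverse events will also be provided". Neither document defines the word 'significant' in this use. SAP section 10, on changes from the protocol's analyses, reads not applicable.

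**What the tables are for.** Protocol 2.5: "The primary hypothesis is that SC evolocumab will be well tolerated when added to standard of care". No numerical criterion is attached, and SAP 9.1 makes all analyses descriptive.

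**The concern.** The trial asks whether evolocumab is well tolerated and has no concurrent control. An overall event rate in one arm is hard to interpret alone, because no comparator shows how much of it would have occurred anyway. Severity and attributed cause are the two routine attributes that help a reader interpret it. Sites are obliged to record both, and the planned adverse event tables use neither.

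The loss runs in both directions. An excess of grade 3 events that were neither serious nor treatment-ending would not be visible. A favourable result, such as no related event of grade 3 or higher, could not be shown from the planned tables either.

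Relatedness also matters elsewhere in the protocol. Under inclusion criterion 103, a treatment-related serious event in the parent study bars rollover, yet treatment-related serious events arising in this study have no table. If such tables are added only after the open-label data have been seen, the choice of what to show is no longer prespecified.

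**Working it through.** The point is textual and the plan gives no power or precision figure for it, so the check sets the planned outputs against the collected attributes.

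**Step 1. Inventory of SAP adverse event outputs (9.6.1, 9.6.2).**

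| Output | By grade? | By relatedness to evolocumab? |
|---|---|---|
| Incidence of TEAEs at week 80 | No | No |
| TEAEs, serious, withdrawal, fatal: overall | No | No |
| The same four by SOC/PT | No | No |
| TEAEs and serious events reaching 1%, by preferred term | No | No |
| Injection site reactions; hypersensitivity | No | No |
| Neurocognitive events | No | No |

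The only CTCAE-graded table in the SAP is the liver function shift table in 9.6.4. It grades laboratory values, not adverse events.

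**Step 2. Trace two hypothetical subjects.** Both have the same injection site preferred term. Subject A's event is grade 1 and judged unrelated to evolocumab. Subject B's is grade 3 and judged related, but is not serious and does not stop treatment. Each counts once in overall TEAEs, once under the same SOC/PT, once under injection site reactions, and once in the 1% list if the term qualifies. Neither appears in the serious, withdrawal or fatal tables. The two subjects are indistinguishable in every row above.

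**Step 3. Protocol 10.4.2 against SAP 9.6.2.**

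| Protocol table | In SAP 9.6.2? |
|---|---|
| TEAEs by SOC/PT | Yes |
| Fatal | Yes |
| Serious | Yes |
| Leading to withdrawal of product | Yes |
| Device related | No |
| 'Significant' TEAEs | No |

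Four of six are carried over, so 6 − 4 = 2 are dropped without an entry in section 10.

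**Step 4. Could the SAP reproduce the protocol's own summary of earlier adolescent data?** Protocol 2.3 reports TEAE and serious event incidences of 71% and 14% in adolescents in Study 20110271. With 14 adolescents in that study, these match 10/14 = 71.4% and 2/14 = 14.3%. It then describes 28 events: "All but 2 of these events were deemed non-serious and were Common Terminology Criteria for Adverse Events (CTCAE) grade 1 or 2", that is 28 − 2 = 26. The two serious events are described as grade 3 and unrelated to the product.

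- TEAE and serious event incidence: the SAP tables would give both.
- Grade of the non-serious events: no SAP table gives it.
- Relatedness of the serious events: no SAP table gives it.

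In those earlier data the events above grade 2 were also the serious ones, so a split by seriousness happened to separate the grades too. The planned tables could not show whether that holds here.

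**The case against.** The strongest reply is that the safety plan is much wider than overall incidence. Withdrawal because of an adverse event is a direct measure of tolerability. Serious and fatal events, injection site reactions, hypersensitivity and neurocognitive events each have a summary. SAP 9.6.3 adds CK, ALT/AST and bilirubin threshold categories. Sections 9.6.4, 9.6.7, 9.6.9 and 9.6.10 add the graded liver shift table, ECG limits, neurologic examination and Cogstate. This stands. A reader might infer that the hypothesis rests only on any-grade, any-cause incidence; the documents do not support that. It does not close the gap, because seriousness is not severity, the adverse event tables in the SAP are all-cause with respect to evolocumab, and the enzyme categories cover only muscle and liver.

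Three further points limit the claim.

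- It would be wrong to say that relatedness is used nowhere. The protocol's device related table uses it, though for the device and not for evolocumab.
- The 'significant' table might use grade or relatedness. The documents do not settle this; the supportable complaint is that the term is undefined and the table is absent from the SAP.
- Protocol 2.3 should not be read as relying on grade and relatedness. It leads with any-cause incidence, adds grade, and mentions relatedness only for the two serious events.

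It can also be said that relatedness is investigator-judged in an open-label study, and that SOC/PT tables in about 10 HoFH subjects will be sparse. Both are true. They are reasons to show the tables beside the all-cause ones, not to omit them. Listings are mentioned generically in SAP 8.7, but 9.6.2 specifies none for adverse events, and a listing is not a summary of incidence.

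**Conclusion.** The point holds in this form: no adverse event table in SAP 9.6.1–9.6.2 is by CTCAE grade or by relatedness to evolocumab, and two protocol tables are dropped without acknowledgement. Under the plan as written, a non-serious event that does not stop treatment is counted identically whether it is grade 3 and related or grade 1 and unrelated.

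The effect is on reporting. Collection, conduct and the other safety outputs are untouched. No numerical size can be given, because the documents do not say how many events will be of grade 3 or higher, or related. The sampling precision of the overall event rate is a different question and does not measure this gap.

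The conclusion assumes that SAP 9.6.1–9.6.2 are the complete list of planned adverse event tables. Their detail, down to sort order, supports that. Nothing here implies that the sponsor or the DMC will not see grade or causality; the DMC charter is outside these documents. The change should be made because it is cheap and bears directly on the trial's primary question.

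**What to change.** Add to SAP 9.6.2, for each of the three groups in section 5.3:

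1. Subject incidence of TEAEs by worst CTCAE grade, with grade 3 or higher by SOC/PT.
2. Subject incidence of evolocumab-related TEAEs and evolocumab-related serious events, by SOC/PT.
3. Injection site and hypersensitivity reactions by worst grade.

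Present all of these beside the all-cause tables, not in place of them. State that the grade is the one recorded on the eCRF: protocol Appendix A names CTCAE version 4.0 for adverse events, while SAP 9.6.4 names version 5.0 or later for the laboratory shift table.

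Then restore the device related and 'significant' TEAE tables, with a definition of 'significant', or record their removal and the reason in SAP section 10.

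The cost is SAP wording and a few standard descriptive tables from data already collected. The downside is small: some sparse cells in the HoFH cohort, and an open-label causality judgement that should be labelled as such.

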9.6.3 Analyses of Secondary Safety Endpoints

Descriptive statistics of change from baseline will be provided for the following safety parameters at week 80.

- Steroid hormone levels (FSH, LH, ACTH, DHEA-S, cortisol, estradiol in females, testosterone in males).
- Carotid intima-media thickness (cIMT)

Summary of subject incidence of abnormal muscle and liver enzymes at week 80 will also be provided.

Abnormalities of muscle and liver enzymes will be assessed by the following categories:

- CK > 5 x ULN
- CK > 10 x ULN
- ALT or AST > 3 x ULN
- ALT or AST > 5 x ULN
- Total bilirubin \geq 2 x ULN
- (ALT or AST > 3 x ULN) and (Total bilirubin > 2 x ULN) and Alkaline Phosphatase < 2 x ULN

Descriptive statistics of change from baseline in growth (height and weight) will be provided at week 24, 48 and 80 by study cohort, parent study treatment and gender.

Shift from baseline in Tanner staging at weeks 24, 48 and 80 will be summarized by study cohort, parent study treatment and gender.

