The interim analysis will be conducted when all the enrolled subjects in the study have opportunity to experience 28 weeks of investigation product exposure or have early terminated from the study. At that time, the database related to the interim analyses of the study will be cleaned, processed and a snapshot will be taken. Unless specified otherwise, the FAS will be the default analysis set in this study. Similar to the primary analysis, the interim data will be summarized by cohort (HeFH and HoFH). Statistical analysis in this interim analysis is descriptive in nature for all safety and efficacy endpoints if applicable. No statistical hypotheses testing, or missing value imputation is planned. There is no study stopping rule for either futility or efficacy and the current design or execution of the study will continue without any changes regardless of the result of the interim analysis.

Analysis of Primary Endpoint

Subject incidence of all treatment emergent adverse events will be tabulated by system organ class and preferred term at week 80. Tables of fatal adverse events, serious adverse events, device related adverse events, adverse events leading to withdrawal from investigational product, and significant treatment emergent adverse events will also be provided. Adverse events will be coded using the latest version of Medical Dictionary for Regulatory Activities (MedDRA).

Analyses of Secondary Endpoints

Growth and pubertal development parameters will be summarized at weeks 24, 48, and 80. Other secondary endpoints will be summarized at week 80. Descriptive statistics will be presented.

An independent DMC which is external to Amgen will formally review the accumulating data to ensure there is no avoidable increased risk for harm to subjects.

For a full description of statistical analysis methods, please refer to [Section 10](#).

[figure not shown]
Sponsor: Amgen

Data Element Standards
Version(s)/Date(s):

Version 5 / 20 March 2015

Approved

Study Design and Treatment Schema

Approved

EOS = End of Study; HeFH = Heterozygous Familial Hypercholesterolemia; HoFH = Homozygous Familial Hypercholesterolemia; IP = Investigational Product; QM = every 4 weeks; SC = subcutaneous

Study Glossary

Abbreviation or Term	Definition/Explanation
ADE	Adverse device effect
AE	Adverse event
AI/Pen	Autoinjector/pen
ALP	Alkaline phosphatase
ALT (SGPT)	Alanine aminotransferase (serum glutamic-pyruvic transaminase)
AMD	Automated mini-doser
ApoA1	Apolipoprotein A-1

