10.1.1.2.2 Secondary Safety Endpoints

- Change from baseline in steroid hormones (FSH, LH, ACTH, DHEA-S, cortisol, estradiol/testosterone [females/males, respectively]) at week 80
- Abnormal muscle and liver enzyme levels (CK, AST, ALT) at week 80
- Change from baseline in cIMT at week 80
- Change from baseline in growth (height and weight) and pubertal development (Tanner staging) at weeks 24, 48 and 80

Approved

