9.6.7 Electrocardiogram

For post-baseline assessments where ECG is performed in triplicate, the average of the 3 (or all available) readings will be used for analysis. Observations with the following diagnosis or findings will be excluded from analysis: artificial pacemaker, atrial fibrillation, atrial flutter, left bundle branch block, and right bundle branch block. PR, QRS, QT, QTc and RR intervals and their change from baseline will be summarized by scheduled visit. Subjects will be categorized and summarized per their maximum post-baseline absolute QTc interval using limits of 450 ms, 480 ms, and 500 ms. They will also be categorized per their maximum change from baseline QTc interval using limits of 30 ms and 60 ms.

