9.6.8 Antibody Formation

The incidence and percentages of subjects who develop anti-evolocumab antibodies (binding and neutralizing) at any time will be tabulated.

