Appendix A. Analytical Study Week Assignments

Selected endpoints will be summarized by scheduled study visits in descriptive analyses. Since the actual visits may not exactly coincide with their scheduled visit day, the actual visit day is mapped to the study visit generally by non-overlapping consecutive intervals covering the entire time continuum, with scheduled visit time being the center of each interval. The mapping intervals for all distinct schedules are summarized in the following tables.

Tests / Analytical Visit Window	Week 4	Week 12	Week 24	Week 36	Week 48	Week 60	Week 72	Week 80
Target day	29	85	169	253	337	421	505	561
Vital Signs (sitting BP, HR)	(1, 56]	(56, 126]	(126, 252]		(252, 448]			(448, EOS]
Physical exam (including neurologic examination)								(1, EOS]
Height, weight, cIMT ^a , Tanner staging			(1, 252]		(252, 448]			(448, EOS]
Neurocognitive assessment (Cogstate battery) - HoFH			(1, 252]		(252, 448]			(448, EOS]
Neurocognitive assessment (Cogstate battery) - HeFH			(1, 364]					(364, EOS]
12 lead ECG								(1, EOS]
Lipids		(1, 210]			(210, 448]			(448, EOS]
ApoA1, ApoB100, Lp(a)		(1, 322]						(322, EOS]
PK (evolocumab), PCSK9		(1, 322]						(322, EOS]
Chemistry, including glucose		(1, 210]			(210, 448]			(448, EOS]
Hematology					(1, 448]			(448, EOS]
Estradiol (females) / testosterone (males)								(1, EOS]
HbA1c, FSH, LH, ACTH, DHEA-S, cortisol, hsCRP, vitamins A/D/E/K								(1, EOS]
CK		(1, 210]			(210, 448]			(448, EOS]
Biomarkers (blood)								(1, EOS]
Anti-evolocumab antibodies								(1, EOS]
HCV viral load					(1, 448]			(448, EOS]
Urinalysis, urine microalbumin, urine creatinine, urine albumin/creatinine ratio								(1, EOS]

^a cIMT assessments conducted up to and including study day 28 are considered baseline values.

Handling multiple records assigned to an analytical study week:

If there is more than one record in a study week interval, the analytical record for that specific study week will be defined as the record closest to the scheduled visit day of that specific study week ($7 \times \text{study week} + 1$). If two records are equidistant from the scheduled day, then the earlier record will be chosen. If there are multiple records on the same day, the last record will be used.

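### As worded, the muscle and liver enzyme table counts threshold crossings at week 80 only, so crossings at weeks 12 and 48 or on early withdrawal draws are left out; transient CK is the main residual gap

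*SAP*

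**What the plan says.** The protocol lists as a secondary safety endpoint (10.1.1.2.2): "Abnormal muscle and liver enzyme levels (CK, AST, ALT) at week 80". Its synopsis, after giving growth and puberty their own visits, adds: "Other secondary endpoints will be summarized at week 80". SAP 9.6.3 carries this through: "Summary of subject incidence of abnormal muscle and liver enzymes at week 80 will also be provided". It then lists the categories:

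- CK above 5 and above 10 times ULN
- ALT or AST above 3 and above 5 times ULN
- total bilirubin at or above 2 times ULN
- a combined ALT/AST, bilirubin and alkaline phosphatase criterion

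Protocol Table 2 schedules post-baseline CK and chemistry at weeks 12, 48 and 80. SAP Appendix A opens with: "Selected endpoints will be summarized by scheduled study visits in descriptive analyses". For CK and chemistry its windows are (1, 210] for week 12, (210, 448] for week 48 and (448, EOS] for week 80. Where several records share a window, "the analytical record for that specific study week will be defined as the record closest to the scheduled visit day". Protocol 7.2.2 asks for the week 80 procedures at withdrawal, if possible.

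Two passages point less clearly to a single visit. Protocol 10.4.3.2 promises an enzyme summary without a time point, and the objective in Protocol 1.3 is subject incidence after 80 weeks of treatment.

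**The concern.** Subject incidence of an enzyme abnormality normally means the number of subjects who ever crossed the threshold on treatment. A single late visit does not give that number when elevations come and go. It also drops subjects who crossed and then left before the week 80 window opened.

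This is a named secondary safety endpoint in children who receive evolocumab on top of lipid-lowering therapy, usually including a statin. If the table is programmed as written, a reader could take a low week 80 count for the 80-week incidence. Two programmers could also read the sentence differently and produce different tables.

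**Working it through.** **1. Reproducing the plan's windows.** Target day = 7 × week + 1, which gives 85, 337 and 561 for weeks 12, 48 and 80. Window limit = midpoint of 7 × week for neighbouring scheduled weeks: (84 + 336)/2 = 210 and (336 + 560)/2 = 448. Both match Appendix A, so the day 448 cut is exact.

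**2. Applying the literal rule to example subjects** (week 80 window, then the record nearest day 561; multiples are of ULN). That the one-record rule governs this table is an inference, because Appendix A covers only selected endpoints.

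| Subject | Counted? |
|---|---|
| CK 12× at day 85, 2× at day 92, normal later | No |
| CK 6× at day 337, 3× on retest at day 344, normal at day 561 | No |
| Withdrawal draw with CK 11× at day 300 or day 448 | No; no week 80 record |
| Withdrawal draw with CK 11× at day 449 | Yes |
| Unscheduled CK 11× at day 500, normal at day 561 | No; day 561 is the retained record |
| CK 6× at day 561, 2× on retest at day 568 | Yes |

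Every subject counted at week 80 also has a post-baseline crossing, but not the reverse. The literal count is therefore at most equal to the any-visit count.

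**3. Size from the documents.** With the stated expected enrollment of 124 and three planned post-baseline draws each: 124 × 3 = 372 draws, of which 124 × 2 = 248 are at weeks 12 and 48, and 248/372 = 67%. The share does not depend on the enrollment figure. It is a share of draws, not of abnormalities.

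**4. Illustration only; the rates are assumptions.** All subjects are taken to have all three draws, and retests are ignored. With a rate of 1% at each draw:

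- Week 80 only: 124 × 0.01 = 1.24 subjects.
- Any visit, fully persistent: 124 × 0.01 = 1.24 subjects.
- Any visit, independent: 124 × (1 − 0.99³) = 124 × 0.0297 = 3.68 subjects.

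The ratio is thus 1 to about 3. Rates rising over the three visits (0.5%, 1%, 3%) give 3.72 subjects at week 80 against 3.72 to 5.52, a ratio of 1.0 to 1.5. Falling rates (3%, 1%, 0.5%) give 0.62 against 3.72 to 5.52, a ratio of 6.0 to 8.9. The ratio is set by the assumed pattern, not by anything in the plan.

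**5. The percentage.** Suppose 10% of subjects have no draw after day 448 (assumed), with a fully persistent 1% rate. The count is 124 × 0.9 × 0.01 = 1.116 against 1.24. Divided by all 124 subjects, the percentage is 0.9% against 1.0%. Divided by the 124 × 0.9 = 111.6 subjects with a week 80 value, it is 1.116/111.6 = 1.0%, the same as 1.24/124. The direction therefore depends on the denominator.

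**The case against.** **The phrase may be cumulative.** SAP 9.6.1 uses the same construction for treatment-emergent adverse events, which accumulate over the treatment period. Together with the objective and the silence of Protocol 10.4.3.2, this makes a through-week-80 count a fair reading. It does not settle the matter. Adverse events have their own period definition in SAP 5.3 and enzymes have none. Within SAP 9.6.3 the same phrase is point-in-time for hormones and cIMT.

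**The SAP's other wording shows little about intent.** A reader might infer a deliberate choice from the contrast with hsCRP ("for levels at baseline to maximum post-baseline value"), QTc ("Subjects will be categorized and summarized per their maximum post-baseline absolute QTc interval") and the count of subjects "who develop anti-evolocumab antibodies (binding and neutralizing) at any time will be tabulated". That goes too far. Each of those has only one scheduled post-baseline visit, so the wording does not follow the visit schedule. The contrast shows only that the authors had cumulative wording available.

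**Other outputs cover much of the ground.** This largely stands:

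- Protocol 9.2.1.1 makes laboratory changes that need treatment or a therapy adjustment adverse events, and the CK rules in Protocol 6.4 feed that route.
- Protocol Appendix A sends concurrent transaminase with bilirubin and/or INR elevation to serious adverse event reporting.
- SAP 9.6.4 has a liver function shift table, although its time basis is not stated.
- SAP 9.6.12 tabulates changes in lipid-regulating medication.
- Protocol 10.1.1.4 makes select safety laboratory values at each scheduled assessment an endpoint. CK is in Protocol Table 3, and the SAP 9.1 statistics include the maximum. If CK is selected, high values at week 12 or 48 would show, though not as subject counts by multiple of ULN.

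What remains is mainly a CK above 5 times ULN that is 5 times or less on retest. Protocol 6.4 then allows IP and statin to be continued, and Protocol 9.2.1.1 generally keeps findings judged not clinically significant out of the adverse event record. CK is not named in the shift table.

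**The SAP follows the protocol, and the stakes are bounded.** Both are true. The study is descriptive, an external DMC reviews accumulating data, and one table is affected. That limits the consequence but does not make the table answer its objective.

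**Conclusion.** The point holds as a defect of wording and method in one secondary safety table. As written, crossings at week 12 or 48, and on retest or withdrawal draws by day 448, are not counted. A later unscheduled crossing is also dropped if another record lies closer to day 561, provided the Appendix A rule applies here. The number of subjects with a crossing can be understated and never overstated. Two thirds of the planned post-baseline draws (248 of 372) cannot contribute.

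Three stronger readings are not supported:

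- **That the percentage is necessarily understated because the FAS is the default set.** An analysis set is not a stated denominator, and with week 80 evaluable subjects the percentage in the example above is unchanged.
- **That the understatement is several-fold.** No abnormality rate is given. At an assumed 1% per draw the comparison is 1.2 against 1.2 to 3.7 subjects, which includes no understatement.
- **That the crossings are lost to the study.** They remain in the data, and many would surface through adverse event reporting or laboratory summaries.

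The conclusion rests on the literal reading. If a cumulative count is intended, the remedy is to say so. Either way it should be settled before the table is produced.

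**What to change.** In SAP 9.6.3:

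- Count subjects whose maximum post-baseline value crosses each threshold. Include scheduled, unscheduled and withdrawal draws through EOS, or through the data cutoff for the interim analysis.
- For the combined liver criterion, use values from the same sample. It requires alkaline phosphatase below a limit, so separate maxima would misclassify subjects.
- State the denominator: FAS subjects with at least one post-baseline value of the analyte.
- State that the Appendix A one-record rule does not apply to this count.
- Keep week 80 as a by-visit row, so that the protocol endpoint as worded is still reported.
- Note the change in SAP Section 10, which now reads as not applicable.

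The cost is a few sentences and a standard derivation with minor programming. No new data are needed. The reported incidence may be less favourable.
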